*** * * Radioisotopes or Radiation Machines * * ***

4) Radioisotopes or Radiation Machines

Please note: For projects requiring radiation procedures, please contact the UA Environmental Health and Safety Office at [name]

a) If applicable, summarize in lay language the radiographic diagnostic and therapeutic procedures associated with this protocol. (X-ray, fluoroscopy, CT, radioactive materials, nuclear medicine, PET-CT, radiation oncology, accelerator, Cyber Knife procedures, etc.).

b) Are the radiation procedures being performed a normal part of the clinical management for the medical condition that is under study (Standard of Care), or are the procedures being performed because the research participant is participating in this project (extra CT scans, more fluoroscopy time, additional Nuclear Medicine Studies, etc.) (Not Standard of Care)? If some procedures are Standard of Care and some are Not Standard of Care, check both boxes.

NOT STANDARD OF CARE

If it is not standard of care, complete the rest of this section. Provide the University of Alabama RSC approval information below.

STANDARD OF CARE

If it is only standard of care, skip the rest of this section.

c) Are research-related radiation procedures limited to X-rays only?

Yes (Complete X-ray table).

No (Skip X-ray table).

d) Total Radiation Exposure (in mRems) from x-ray procedures:

To calculate radiation exposure from x-rays only, University of Alabama allows use of the Duke University Radiation Safety Committee dose estimate calculator. University of Alabama does not allow use of this website to calculate any other type of radiation exposure.

To determine the dose estimate, click on the appropriate links, below (you will be taken to the Duke University Radiation Safety Committee website). Enter the x-ray procedures into the appropriate fields of the website and click "create statement". Enter the dose estimate from the statement in the table above.

For studies involving adults, please click [here](#).

For pediatric studies, please click [here](#).

e) Please list all radiation procedures (including x-ray) that are research-related (not standard of care). Include the anatomical location and specify the number of times that each procedure will be conducted throughout the entire study.

NOTE: The IRB will determine if this study requires radiation safety review by the Radiation Safety Officer or the Radiation Safety Committee.

For more information on how to submit for radiation safety review, contact the Radiation Safety Officer.

*** * * Drugs, Reagents, Chemicals, or Biologic Products * * ***

5. Drugs, Reagents, Chemicals, or Biologic Products

Pilot	Phase I	Phase II
Phase III	Phase IV	Not Phased

- a) Please list in the space below all investigational drugs, reagents or chemicals to be administered to participants during this study.
- b) Please list in the space below all FDA approved drugs, reagents, chemicals to be administered to participants during this study.

Please read the IND Statement 1 and IND Statement 2.

*** * * Devices * * ***

6. Devices

- a) Please list in the space below all investigational devices to be used on participants during this study.
- b) Please list in the space below all FDA approved devices to be used on participants during this study.

*** * * Subject Population(a-h) * * ***

7. Subject Population - In the space below, please detail the participants that you are requesting to recruit (include description of each group requested)

a) Expected age range of participants. (For example - 19 yrs to 90 yrs).

Participants with Down syndrome will be between 10 and 30 years of age.

Typically developing children will be between 4 and 9 years of age.

We will test 48 participants per group - plus an additional 6 typically developing children as needed to provide a closer match on nonverbal ability for the children in the Experimental condition with the children in the control condition.

b) i) Number to be directly solicited for this research.
 
ii) Number to be consented (including withdrawals or screen failures)
 
iii) Number expected to complete the study.
 
c) If this is multi-center study, number of participants to complete the study study-wide
 
d) If study involves review of medical or other records, number of records to be reviewed.
 
e) If women, minorities, or minors are excluded, a clear compelling rationale must be provided unless not applicable. Examples for not including minors: disease does not occur in children; drug or device would interfere with normal growth and development; etc.
 
f) Describe how potential participants will be identified for recruitment (e.g., chart review, referral from individual's treating physician, those individuals answering an ad). How will potential participants learn about the research, and how will they be recruited (e.g., flyer, e-mail, web posting, telephone, etc.)? State where recruitment materials will be located. Click "Add" to upload recruitment materials document.
	
X N/A
 
N/A
 
102
 
102
 
N/A
 
102
 
X N/A
 
NA

--	--

Important to remember: Study Activities cannot begin until IRB approval is granted.

General Information: Potential recruitment sites are identified and we provide them with information about the study. We ask them to identify potential participants and to send recruitment and consent information to the parents/guardians of the identified individuals. We do not get any identifying information on individuals at this point in time. Participants self-identify to the researchers by returning signed consent forms with contact information or by requesting additional information about the study. We will not contact any individuals who have not identified themselves as interested in the study. Information to be discussed with recruitment sites and a draft letter for them to send to parents/guardians is attached.

The University of Alabama participants with DS will be recruited from the University of Alabama Intellectual Disabilities Participant Registry that was established with NICHD Recovery Act Funding ([name], PI). Participants will also be recruited through local DS organizations like DS Alabama, DS Connect, and through local public schools. Montclair State University participants with DS will be recruited from local service providers, DS Connect, and local public schools. The lead PI at Montclair State has established research relationships with these organization in the past several years. Twenty-four participants will be tested at UA and 24 at Montclair State University.

Typically developing children will be recruited from local preschools and elementary schools, including The University of Alabama Children's Program and the Montclair State University preschool program. Twenty-seven participants will be recruited from each site.

We have secured permission from the CDRC (see attached permission email) and recruited typically developing children from that site. We are adding the following organizations for recruitment and will be contacting them about recruitment following approval of the new recruitment materials. We will be identifying additional recruitment sites in the future that will be added to the list once contact is made.

<https://childrenhelpingscience.com/>
Massachusetts Down Syndrome Congress
Global Down Syndrome Organization
New Jersey Down Syndrome Organization

The new recruitment materials include Flyers and access to the PIs research web page. These are attached to the current protocol for review. [name]'s research web page is visible for a short time if you would like to view it formatted. Organizations have not been invited to view the page prior to approval. The Web Page address is:
<[name]>

Letters of support from organizations assisting with recruiting efforts will be provided to the IRB. WE have attached an email approving recruitment from The University of Alabama CDRC.

*** Subject Population(i-l) ***

7. Subject Population (continued)

i) Inclusion and Exclusion Criteria.

Identify inclusion criteria.

All participants must meet the following enrollment criteria based on parental report: (1) adequate vision for tasks in this study, (2) adequate verbal skills for understanding instructions for tasks, and (3) no accompanying diagnoses of Autism Spectrum Disorder as autism symptomology could confound results.

Identify exclusion criteria.

No additional exclusion criteria are established.

j) **Compensation.** Explain the amount and schedule of compensation, if any, that will be paid for participation in the study. Include provisions for prorating payment.

Participants will receive a Tablet computer (Valued at Approximately \$75) and \$100 for completing the study. If a participant cannot complete the study, they will receive payment at the rate of \$25 dollars for starting each of the four months of the study.

If approved, we will be offering parents and parents to complete the project in less time by increasing the number of experience activities completed each week. If parents choose this option, they will be paid \$25 for completing each 25% of the scheduled activities (4 experiences with each of the 4 activities).

k) **Describe who will cover study related costs.** Explain any costs that will be charged to the participant. Include provisions for prorating payment.

There are no costs to participants.

l) **Estimate the probable duration of the entire study including data analysis and publication.** This estimate should include the total time each participant is to be involved and the duration the data about the participant is to be collected. If the study is Investigator-initiated, a timeline for individual participant recruitment, follow-up, total time for participant accrual, and data analysis for the study is required.

Each participant will be enrolled for approximately 17 weeks following completion of the consent process. This translates into two sessions per week, with two experience activities per session. We now believe the activities will take approximately 10 minutes per session. (Participants will be recruited on a rolling schedule, with different participants recruited and tested throughout the duration of the study. Data collection for the study is projected to take approximately 3 years. Data analysis and publication should take place in the year following data collection - for a total time of 4 years.

Initial participants have inquired about the flexibility of this schedule. From a research integrity perspective, we believe it is feasible to conduct the study in less time per person if they are willing and able to complete additional experience activities during each week. We would like to provide participants with the option of completing up to twice as many activities during each week - reducing time to complete the study by half. This can be done by increasing the number of sessions per week or increasing the number of activities per session. Care will be taken to ensure that participants do not become fatigued during these sessions. We will complete no more than twice the activities in any given session, and no more than twice the number of sessions per week.

*** * * Subject Population(m) * * ***

Research Involving Children

NOTE: Investigators, please include this information with the e-Protocol application if your research involves children. In Alabama a child is an individual less than 18 years of age unless the child is legally emancipated. If your research involves children with more than one vulnerability (e.g., children who are pregnant, incarcerated, or cognitively impaired) attach the supplementary information for that vulnerable population as well.

Minimal risk means that the probability and magnitude of the harm or discomfort anticipated in the research are not greater in and of themselves than those ordinarily encountered in daily life of a healthy child or during the performance of routine physical or psychological exams or tests.

Section 1.

Select and complete the category that applies to your research.

Category 1 (45 CFR 46.404; 21 CFR 50.51)

My research does not involve greater than minimal risk.

a) **My research falls under this category because:**

My research involves research on individual or group characteristics or behavior (including perception, cognition, language, social behavior, etc.) or research employing survey, interview, focus group, program evaluation, human factors evaluation, or quality assurance methodologies. The probability and magnitude of the harm or discomfort anticipated in the research are not greater in and of themselves than those ordinarily encountered in daily life of a healthy child or during the performance of routine physical or psychological exams or tests. No deception is involved.

b) Describe what provisions will be made for soliciting the assent of the children, and the permission of both parents, or the legal guardian. (Permission from both parents must be obtained unless one parent/guardian is deceased, unknown, incompetent, or not reasonably available, or when only one parent/guardian has legal responsibility for the care and custody of the child). Justify reason(s) if seeking permission from only one parent.

Parents will be sent information about the study and signed consent is required prior to asking children to participate. Children will be told about the study and will be included only if they assent to volunteer for the study.

We only plan to obtain signed consent from one parent for the following reasons. First, the study is minimal risk and only requires that participants engage in behaviors similar to those of their daily lives. Second, we do not have the means to firmly establish family status for families of participants to determine if both parents are available for consent. Third, and most importantly, the failure to include participants of families without two parents available to consent will render the sample ungeneralizable to the population as a whole and have the likely and inadvertent effect of disproportionately eliminating potential participants from minority and lower SES groups.

Category 2 (45 CFR 46.405; 21 CFR 50.52)

My research involves greater than minimal risk but presents the prospect of direct benefit to the individual participants.

a) **My research falls under this category because:**

b) **Justify the risk(s) by explaining the anticipated benefit to the participants:**

c) **Explain how the relation of the anticipated benefit to the risk is at least as favorable to the participants as that presented by available alternative approaches:**

d) **Describe what provisions will be made for soliciting the assent of the children, and the permission of at least one parent/guardian. (Permission from both parents must be obtained unless one parent/guardian is deceased, unknown, incompetent, or not reasonably available, or when only one parent/guardian has legal responsibility for the care and custody of the child). Justify reason(s) if seeking permission from only one parent.**

Category 3 (45 CFR 46.406; 21 CFR 50.53)

My research involves greater than minimal risk, and no prospect of direct benefit to individual participant, but likely to yield generalizable knowledge about the participant's disorder or condition.

a) **My research falls under this category because:**

b) Describe how the risks for participating in your research represent a minor increase over minimal risk (i.e., the children being recruited have a disorder or condition that would place them in a group other than an average healthy child; therefore, the research qualifies as a minor increment over minimal risk. This risk is slightly more than what the average healthy child would experience, but is reasonable for these participants because it is not more than they would experience or expect given their condition.).

c) Describe how the research intervention(s)/procedure(s) present experiences to participants that are reasonably commensurate to those inherent in their actual or expected medical, dental, psychological, social, or educational situations:

d) Explain why the intervention or procedure is likely to yield generalizable knowledge about the participants' disorder or condition, which is of vital importance for the understanding or amelioration of the participants' disorder or condition:

e) Describe what provisions will be made for soliciting the assent of the children, and the permission of both parents/guardians. (Permission from both parents must be obtained unless one parent/guardian is deceased, unknown, incompetent, or not reasonably available, or when only one parent/guardian has legal responsibility for the care and custody of the child). Justify reason(s) for seeking permission from only one parent.

Category 4 (45 CFR 46.407; 21 CFR 50.54)

My research does not fall under Category 1, 2, or 3 listed above. However, the research presents a reasonable opportunity to understand, prevent, or alleviate a serious problem affecting the health or welfare of children.

(NOTE: If your research is funded by, or funding has been sought from the Department of Health and Human Services (DHHS), Department of Education, or is FDA regulated, a report must be sent for review to the DHHS Secretary, Secretary of the US Department of Education, or Commissioner of FDA. If this category is applicable, the Office of Research Compliance will prepare and submit a report of IRB review to the appropriate federal official(s)).

a) My research falls under this category because:

b) Describe what provisions will be made for soliciting the assent of the children, and the permission of both parents/guardians. (Permission from both parents must be obtained unless one parent/guardian is deceased, unknown, incompetent, or not reasonably available, or when only one parent/guardian has legal responsibility for the care and custody of the child). Justify reason(s) if seeking permission from only one parent.

Section 2.

In order to effectively assess and evaluate the risk of your proposed research to children, the IRB requires the following information. Respond to all items.

a) Provide justification for the participation of children as research participants in your study.

The children used in this study are necessary for providing a comparison group matched on non-verbal ability with participants with Down syndrome. In this type of research, it is necessary to evaluate the performance of individuals with Down syndrome against participants who are matched on general ability measures to determine if the difficulties associated with Down syndrome are beyond that which would be expected based on developmental level.

b) Has this research been conducted in adults? Y

If yes, is there any indication that the proposed research would benefit, or at least not be harmful to children?

Similar research has been conducted in adults and children with no adverse effects. The children are essential for providing a comparison group for the participants with Down syndrome.

c) Indicate how many children you propose to enroll in the study and justify this number (whenever possible, involve the fewest number of children necessary to obtain statistically significant data which will contribute to a meaningful analysis relative to the purpose of the study).

All of the typically developing participants will be children (48 participants originally planned). Many of the participants with Down syndrome will also be participants (we anticipate about half of the 48 participants in this group, or 24). The total number of participants was determined by power analysis. A 4 groups x 3 repetitions analysis with alpha set at .05, power set at .80, and total N = 96 (24 in each group) would be sufficient to observe a significant effect size (f(V)) of .27 or greater. To evaluate the power for simple effects tests to compare the effects of training for the DS and TD participants separately, we conducted a 2 groups (Delay and No Delay) x 3 repetitions analysis with alpha set at .05, power set at .80, and total N = 48 (24 in each group). Power analysis indicated that 48 total participants would be sufficient to observe a significant effect for effect sizes (f(V)) of .27 or greater for main effects of Delay and of .25 or greater for main effects of Assessment Time. Power calculations were conducted in GPower 3.1.9.2 (Faul et al., 2007). However, we are requesting an additional 6 typically developing participants at this time to make it possible to better match the Experimental and Control group children on nonverbal ability.

d) Describe how assent of a child will be obtained and documented (if applicable). If not applicable, explain why.

The different procedures will be described to the participant at the start of each session. They will then be asked if they want to take part in the current day's activities. We will only continue if the participant agrees to continue. We will record whether or not assent was given on our daily record sheet before continuing on each day.

I am requesting waiver of the requirement for assent.

Justify:

OR

I have attached an assent form/assent script for IRB review.

Y

e) Explain what methods will be used for evaluating dissent (i.e., description of behaviors that would indicate child does not want to participate (such as moving away, certain facial expressions, head movements, etc...)).

If children indicate they do not want to perform the activities or appear reluctant to perform the activities by resisting, frowning, shaking their heads, etc.) we will discontinue the activities for the day. If they appear reluctant to continue for multiple sessions (i.e., two in a row without explanation) they will be discontinued from the study.

f) Describe how parental permission will be obtained. [Note: If you propose to waive the requirement for parental permission (i.e., getting parental permission may be against the best interest of the child, i.e., a study of abused or neglected children), describe what measures will be taken to protect the rights and welfare of the children.]

The study consent will be sent to parents and they will be asked to return it via mail or in person. They will be given the opportunity to call the PI to request additional information. Participants will be asked to be in the study only after a signed consent has been

returned to the experimenter.

I am requesting waiver of the requirement for parental permission.

Justify:

OR

I have attached a parental permission form for IRB review.

Y

g) Describe measures that will be taken to ensure that a parent is present when the child participates in any research interventions or procedures. [Note: If the nature of the research is such that it is not appropriate to have a parent present (i.e., research into sensitive personal issues, physical examinations of teenagers, etc...) please explain why.]

Parents will be required to be in the home or on campus when their children are tested to ensure their presence in case of an emergency. If the parent cannot be present, testing will be rescheduled.

h) Describe the expertise of the research staff/study personnel for dealing with children at the ages included and whether they are knowledgeable and sensitive to the physical and psychological needs of the children and their families. Describe the appropriateness of facility in which the research will be conducted in relation to environment and/or equipment accommodating to children.

Drs. [name], [name], and [name] have been conducting research with children for many years and are knowledgeable and sensitive to the needs of child participants and families. All Graduate and Undergraduate student Research Assistants will be trained by these faculty. Before they will be allowed to conduct the project on their own, they will participate in sessions with the faculty, and then observed by the faculty when they first take the lead role in conducting the sessions. Two RAs will be present during all testing sessions as an added measure to ensure that the needs of participants are met. We anticipate that most sessions will take place in the participants home. When taking part on campus, rest room facilities and a break area with approved snacks will be provided as needed.

i) If applicable, provide any additional information that may support your request to involve children in this research.

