Specific Aim 1 evaluates the malleability of MR and PT performance in participants with DS. Consistent with Aim 1, we will apply Multivariate ANOVA to the subsample of DS children. If the test for sphericity is significant, we will interpret the multivariate tests for the within subject effects. If not, we will use the univariate tests due to their increased statistical power. With either option, the test for the effect of Assessment, if significant, would indicate that performance of the DS children improves over time. We will then evaluate the interaction of AssessmentDelay, which if significant would signify that Delay vs No Delay participants exhibit a different magnitude of improvement across Assessment times. One contrast of interest compares Delay vs No Delay participants at Assessment 2. Performance favoring the No Delay participants would indicate a significant effect of spatial ability experience. A second contrast of interest compares Assessment 3 performance to Assessments 1 and 2 for the Delay participants. If we are able to confirm that the Delay participants exhibit higher scores at Assessment 3 than at Assessments 1 and 2 (which should not differ) then the benefits of spatial ability experience for persons with DS would be further confirmed.

Specific Aim 2 evaluates possible differences in rate and magnitude of improvement of DS and TD participants. We will approach Aim 2 in a very similar statistical manner. For Aim 2a, we will apply Multivariate ANOVA to the whole sample to test for the effect of AssessmentGroup. If significant, it is indicative that DS and TD participants do not exhibit the same degree of improvement following training. If improvement in performance is greater for the participants with DS, it

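### The two N = 48 detectable effects labelled f(V) do not give 80% power on the scale that reproduces the N = 96 figure; they look like correlation-based f, with no correlation stated

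*Combined protocol and SAP*

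**What the plan says.** The sample size justification is in Subject Population(m), Research Involving Children, Section 2(c). It reports two calculations from GPower 3.1.9.2.

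- **Whole sample.** The design and inputs are given as "A 4 groups x 3 repetitions analysis with alpha set at .05, power set at .80, and total N = 96 (24 in each group"). The effect being tested is not named. The stated conclusion is that this sample "would be sufficient to observe a significant effect size (f(V)) of .27 or greater".
- **DS and TD separately.** For the simple effects, the text says "we conducted a 2 groups (Delay and No Delay) x 3 repetitions analysis". The inputs for this second calculation are "alpha set at .05, power set at .80, and total N = 48 (24 in each group"). It concludes that 48 participants suffice for "effect sizes (f(V)) of .27 or greater for main effects of Delay and of .25 or greater for main effects of Assessment Time".

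All three effect sizes carry the label f(V). No correlation between repeated assessments is stated there, in the analysis text (Study Procedures, 3(d)), or elsewhere in the published form. The attachments list includes a grant proposal whose text is not part of the form.

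Section 3(d) plans a multivariate ANOVA of the DS subsample for Aim 1. If sphericity is not rejected: "If not, we will use the univariate tests due to their increased statistical power".

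**The concern.** Halving the sample, with the same alpha and power, ought to raise the detectable effect. Here it stays at .27 for Delay and is .25 for Assessment Time. The tests differ in degrees of freedom, so this alone proves nothing, but it is reason to recompute.

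The N = 48 sentence is the only stated power support for analysing the two groups separately, and Aim 1 is a DS-only analysis. A reader who takes the label at face value will credit that analysis with 80% power at f(V) of .25 to .27, and may read too much into a null result. A reader who suspects correlation-based f cannot check the figures without the correlation.

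**Working it through.** **Inputs.** From Section 2(c): alpha .05, power .80, m = 3 assessments; N = 96 in k = 4 groups; N = 48 in k = 2 groups. Power is the upper tail of a noncentral F with noncentrality λ.

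**1. Reproduce the N = 96 figure on the f(V) scale.** For the groups by repetitions interaction, s = min(m − 1, k − 1) = 2, df1 = 2 × 3 = 6, df2 = 2 × (96 − 4 − 2 + 2) = 184, and λ = N × s × f(V)².
- At .27: λ = 96 × 2 × 0.0729 = 14.00, power 79.7%.
- For 80% power: λ = 14.10, f(V) = √(14.10/192) = 0.271. This matches.
- The other f(V) tests do not match: the four-group effect (df 3, 92) needs 0.344 and Assessment (df 2, 91) needs 0.322.

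The interaction is therefore inferred to be the effect behind .27.

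**2. N = 48 on the same scale**, with s = 1 and λ = N × f(V)².

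| Effect | df | λ at printed value | Power | λ for 80% | f(V) for 80% | N for 80% at printed value |
|---|---|---|---|---|---|---|
| Delay, .27 | 1, 46 | 48 × 0.0729 = 3.50 | 44.9% | 8.19 | √(8.19/48) = 0.413 | 110 |
| Assessment, .25 | 2, 45 | 48 × 0.0625 = 3.00 | 30.3% | 10.31 | √(10.31/48) = 0.463 | 158 |

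Variants do not rescue the figures (Delay, then Assessment): λ based on error df, 43.4% and 28.6%; alpha .10, 57.9% and 42.8%; N = 96, 74.5% and 56.9%. A univariate effect size without a correlation gives 56.9% for Assessment.

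**3. N = 48 as correlation-based f**, with common correlation ρ.
- Delay: λ = N × f² × 3/(1 + 2ρ).
- Assessment: λ = N × f² × 3/(1 − ρ), df 2, 45 (multivariate) or 2, 92 (univariate).

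| Assumed ρ | Delay: f for 80% | Delay: power at .27 | Assessment (multivariate): f for 80% | Assessment: power at .25 |
|---|---|---|---|---|
| 0.12 | 0.266 | 81.3% | 0.251 | 79.7% |
| 0.13 | 0.268 | 80.7% | 0.250 | 80.2% |
| 0.16 | 0.274 | 78.8% | 0.245 | 81.6% |
| 0.5 | 0.337 | 61.1% | 0.189 | 96.5% |

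Allowing for rounding, Delay = .27 needs ρ of 0.117 to 0.165. Assessment = .25 needs 0.091 to 0.161 (multivariate) or 0.059 to 0.132 (univariate). The overlap is 0.117 to 0.161, or 0.117 to 0.132.

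**4. Can one relabelling cover all three figures?** At ρ = 0.12 to 0.16, correlation-based f for N = 96 and 80% power is:
- interaction, λ = 96 × 3 × f²/(1 − ρ), df 6, 184: 0.208 to 0.203;
- Assessment, same form, df 2, 91: 0.174 to 0.170;
- group, λ = 96 × 3 × f²/(1 + 2ρ), df 3, 92: 0.221 to 0.228.

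None is .27.

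**5. Tests named in 3(d) but not in the power text.** Assessment by Delay at N = 48 has df 2, 45, so its detectable f(V) is also 0.463. An unadjusted comparison of 24 v 24 at Assessment 2 needs 2 × √(8.19/48) = 0.83 SD.

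**The case against.** The strongest reply is that the N = 48 figures are sound and only the symbol is wrong. One correlation near 0.13 gives close to 80% power for both effects, a coincidence that is hard to explain otherwise, and the value may be in the grant proposal. This largely stands. A reader might infer from 45% and 30% that the separate-group analyses were planned with inadequate power. The documents do not support that: those percentages hold only if the label is right, and the likelier reading is that it is not. The reply still leaves a wrong label and figures that cannot be checked from the published form.

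Three further limits also stand.
- Section 2(c) does not name the N = 96 effect, so the f(V) calibration is an inference.
- A reader might infer that no relabelling could reconcile the paragraph. That is shown only for one common correlation; with separate correlations, the N = 96 group effect alone gives f = 0.27 at about 0.42.
- The sentence claims power only for the two main effects. A reader might treat the missing interaction figure as part of the error, or take the interaction as the plan's test of experience. Section 3(d) says of the interaction: "which if significant would signify that Delay vs No Delay participants exhibit a different magnitude of improvement across Assessment times". It ties the experience effect to another comparison: "One contrast of interest compares Delay vs No Delay participants at Assessment 2". Figures for either would be extra reporting.

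Finally, the total of 96 rests on a figure that reproduces, and accrual is closed.

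**Conclusion.** The N = 48 sentence is wrong as labelled. On the f(V) scale inferred from the N = 96 figure, it claims 80% power where the design gives 45% (Delay) and 30% (Assessment Time); 80% needs 0.41 and 0.46. The probable cause is correlation-based f printed as f(V), with a correlation near 0.13, which the documents do not confirm. If so, the defect is a wrong unit and an input not stated in the published form, and the result is sensitive to that input. The three figures cannot share one label under one common correlation.

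All of this describes the planned 48 per group. The continuing review form (item 5) reports 30 DS participants consented, so neither the printed nor the corrected figures describe the DS sample as accrued. The arithmetic is firm; which of the two explanations applies is for the sponsor to say.

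**What to change.** In Section 2(c), correct the N = 48 sentence in one of two ways.

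- **(a)** Restate the detectable effects as f(V) = 0.41 for Delay and 0.46 for Assessment Time.
- **(b)** Relabel them as correlation-based f, state the correlation assumed and whether the test is multivariate or univariate, and keep .27 and .25 only if that correlation gives them.

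Naming the effect behind the N = 96 figure would remove the need to infer it.

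Optional: add that Assessment by Delay has the same detectable f(V) as Assessment (0.46), and that the Assessment 2 contrast needs about 0.83 SD in an unadjusted 24 v 24 comparison.

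The cost is a sentence or two. Under (a) the stated sensitivity looks less favourable; under (b) a unit changes and an input is disclosed. Enrolment and analysis do not change.
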